## PROTOCOL SUMMARY

Title	A Multicenter Phase II Study of Maintenance Belantamab Mafodotin (Blenrep®) after BCMA-Directed Chimeric Antigen Receptor T-cell Therapy in Patients with Relapsed and/or Refractory Multiple Myeloma (RRMM)						
IND Sponsor	Sponsor-investigator						
Principal Investigator	[name]						
Anticipated Study Sites	Three (including MCW)						
Clinical Trial Phase	Phase II						
Study Disease	Relapsed and/or refractory multiple myeloma						
Main Inclusion Criteria	
 
Diagnosis of multiple myeloma with measurable disease (at the time of diagnosis: serum M-protein ≥ 0.5 g/dL or urine M-protein ≥200 mg/24 hours or involved serum-free light chain ≥10 mg/dL provided that the ratio of involved/uninvolved light chain is abnormal) prior to receiving anti-BCMA CAR-T. Patients with no biochemically measurable disease prior to CAR-T may be enrolled if bidirectionally measurable plasmacytomas or bone marrow plasmacytosis ≥10% are present prior to CAR-T infusion.
 
Received at least four prior lines of therapy (including a PI, IMiD, and anti-CD38 monoclonal antibody – note radiation therapy is considered a line of therapy) before BCMA-targeted CAR-T, and has not progressed/relapsed after receiving CAR-T therapy.
 
Achieved at least SD as a response to CAR-T therapy and remained progression-free after anti-BCMA CAR-T administration until enrollment (this requirement is also necessary prior to administration of first study drug).
 
						
Main Exclusion Criteria	
 
Prior exposure to belantamab mafodotin before enrollment on the trial, including before administration of anti-BCMA CAR-T.
 
Evidence of progression/relapse after BCMA CAR-T before enrollment (this requirement is also necessary prior administration of first study drug).
 
Subject has achieved CR/sCR at the time of enrollment (this requirement is also necessary prior to administration of first study drug).
 
Subject was given BCMA CAR-T under EAP (expanded access protocol) for non-conforming product.
 
Subject progressed on a prior anti-BCMA therapy before receiving commercial anti-BCMA CAR-T.
 
Any previous treatment-related adverse events higher than grade 1 at enrollment (except for alopecia and grade 2 neuropathy).
 
Acute active infection requiring treatment within 14 days of enrollment (this requirement is necessary also prior to administration of first study drug).
 
Current or prior involvement of the central nervous system by multiple myeloma.
 
Smoldering multiple myeloma or POEMS.
 
						
Primary Objectives	To describe 12-month progression-free survival (PFS) of patients receiving belantamab mafodotin as maintenance therapy (every eight weeks) after anti-BCMA CAR-T administration for relapsed/refractory myeloma.						
Primary Endpoints	12-month conditional PFS, defined as the probability of being alive without progression/relapse or death at 12 months from the time of CAR-T administration conditional on being alive without progression/relapse at 3 months from the time of CAR-T.						

[figure not shown]
Short Title: MCW EMBRACE TRIAL 7 Version No.: 3
Version Date: 12/29/2022

Secondary Objectives	
 
To describe the toxicity profile of belantamab mafodotin given as maintenance after CAR-T.
 
To describe progression-free survival.
 
To describe changes in International Myeloma Working Group (IMWG) response category for patients not in CR when initiating therapy with belantamab mafodotin as post-CAR-T maintenance.
 
To identify the rate of elimination of minimal residual disease (MRD) (≤10–5) in patients with myeloma at baseline and after starting belantamab mafodotin as post-CAR-T maintenance (at screening/baseline, after two, six, and 12 cycles).
 
Patient-reported quality of life studies (QoL).
 
To describe the overall survival (OS) for the entire cohort from the time of CAR-T administration.
 
					
Secondary Endpoints	
 
Best objective response on the trial (by IMWG criteria).
 
Progression-free survival.
 
Negative MRD (≤10^-5, by clonoSEQ®), including imaging plus MRD-negativity (≤10^-5 in bone marrow and no area of PET-CT FDG uptake greater than mediastinal blood pool or surrounding normal tissue).
 
Duration of response on maintenance.
 
Time to progression/relapse after CAR-T.
 
Overall survival for the entire study population.
 
Adverse events on the trial.
 
QoL parameters.
 
					
Exploratory Objectives	Exploratory: BCMA expression by flow cytometry and soluble     BCMA/BAFF/APRIL levels will be monitored at screening/baseline, and     after two, six, and 12 cycles.					
Exploratory Endpoints	Baseline and on-treatment sBCMA/BAFF/APRIL and BCMA expression on myeloma cells.					
Study Design	This is a multicenter phase II, open-label study evaluating the efficacy and safety of belantamab mafodotin maintenance in participants with RRMM who have received commercially available anti-BCMA CAR-T-cell therapy.  Subjects will be enrolled 60–120 days after CAR-T and receive belantamab mafodotin as maintenance therapy. Although screening can occur as early as day 60 post CAR-T therapy, study treatment cannot be started prior to day 90 post CAR-T therapy. Each maintenance cycle will have a duration of 56 days (+/- three days) and belantamab mafodotin will be administered at a dose of 1.9 mg/kg IV on day 1 of each cycle. The study will enroll up to 45 subjects with an interim analysis performed when 23 patients have been treated and followed to the 12th month after					
Study Intervention Description	Subjects will receive belantamab mafodotin as maintenance therapy. Belantamab mafodotin will be administered IV over approximately 30 minutes at the recommended dose of 1.9 mg/kg IV on day 1 of every eight-week (+/- three days) cycle. Maintenance therapy with belantamab mafodotin will continue until progressive disease (PD), death, unacceptable toxicity, withdrawal of consent or end of study, whichever occurs first. Dose interruptions or reductions may be required to address potential drug-associated toxicities. The dose to be administered will be based on actual body weight calculated at baseline. However, if the change in body weight is greater than 10%, the dose will be recalculated based on the actual body weight at the time of dosing. The dose may be reduced to address toxicity, as described in Section 5.3.					
Number of Subjects	Total sample size for this phase II study will be 45 patients. The sample size was computed to achieve 80% power at a one-sided 5% significance level to detect an increase in 12-month conditional PFS to 74% from the historical value of 54%. This corresponds to raising the 12-month unconditional PFS from 40% to 55%.					

Short Title: MCW EMBRACE TRIAL 8 Version No.: 3
Version Date: 12/29/2022

Estimated Time to Complete Enrollment:	Approximately three years.
Estimated Time to Study Completion:	Ten years (~3 years enrollment, ~2 years for completion of treatment for all patients, and ~5 years of long-term survival follow-up)

### STUDY SCHEMA

**Table 1. STUDY CALENDAR (SCHEDULE OF ACTIVITIES)** 

Study Assessments	Screenin g 	C1D1 (56 days) 	C2D1 (56 days	C3D1 (56 days	C4D1 (56 days	C5D1 (56 days	C6D1 (56 days	C7D1 (56 days	C8D1 (56 days	C9D1 (56 days	C10D 1 (56 days	C11D 1 (56 days	C12D 1 (56 days	70-day post- last dose Safety Visit 	Pre - Progre ssion Q3 mo 	LTF U (Q6 mo) 
Visit window	Day -30 to enrollme nt		+/- 3 days	+/- 3 days	+/- 3 days	+/- 3 days	+/- 30 days	+/- 30 days								
Informed consent	X															
H&P	X	X	X	X	X	X	X	X	X	X	X	X	X	X	X	
Ocular exam 	X		X	X	X	X	X	X	X	X	X	X	X	X	X	$\mathbf{x}^2$
ECOG Performance Status	x	x	x	x	x	x	x	x	x	x	x	x	x	X	X	
Adverse events/SAEs collection/reporti ng 	x	X	X	x	X	X	X	X	X	X	X	X	X	X		
Concomitant medications 	X	X	X	x	X	X	X	X	X	X	X	X	X	X		
Vital signs (BP, HR, body temperature)	X	x	X	x	X	x	x	x	x	x	x	x	X	X		
Height	X															
Body weight	X	X	X	X	X	X	X	X	X	X	X	X	X		X	
Hematology 	X	X	X	X	X	X	X	X	X	X	X	X	X	X	X	
Chemistry 	X	X	X	X	X	X	X	X	X	X	X	X	X	X	X	
eGFR by MDRD	X	X	X	X	X	X	X	X	X	X	X	X	X	X		
HbsAg, HbcAb, and hepatitis C antibody. hepatitis C RNA 	x															
Pregnancy test for WOCBP 	х	x	х	x	х	Х	X	х	х	х	х	х	Х	X		
12-lead ECG	X															

Short Title: MCW EMBRACE TRIAL

11

Version No.: 3

Version Date: 12/29/2022

Echocardiogram or MUGA for LVEF	Х														
24-hour urine protein electrophoresis 	х	x		X		X		X		X		X	X	X	
Urine immunofixation 	X	X		X		X		X		X		X	X	X	
Serum immunofixation	X	X	X	X	X	X	X	X	X	X	X	X	X	X	
SPEP	X	X	X	X	X	Х	X	X	X	X	X	X	X	X	
Quantitative IgG, IgM, IgA	Х	X	Х	X	х	X	Х	Х	Х	х	Х	х	X	X	
β2-microglobulin	X														
Serum kappa, lambda free LC, FLC ratio	X	x	X	Х	Х	х	х	X	X	Х	X	Х	X	X	
Imaging for bone (lytic) lesions: skeletal survey, CT or PET-CT 	х						х						X		
Imaging (whole- body PET-CT or CT or MRI) if history of extramedullary disease 	x						х						х		
Whole-body PET-CT 	X 														
BM aspirate/biopsy for disease assessment  and 	x 		x 				x 						x 		
BM for FISH testing 	Х												Х		
NGS for MRD (ClonoSEQ®) 	x^		x^				x^						x^		
Correlatives: BM aspirate sample flow cytometry and cytotoxicity assays	x		X				x						X		
Correlatives: Soluble	X		x				x						X		

BCMA/BAFF/AP RIL (serum)																
Premedication if needed		X	X	X	X	Х	X	X	X	X	X	X	X			
Belantamab mafodotin IV administration		X	X	X	X	X	X	X	X	X	X	X	X			
Preservative-free artificial tears		Х	X	X	X	х	Х	Х	X	X	Х	Х	X			
PRO questionaires 		Х	Х	Х	Х	х	Х	Х	Х	х	Х	х	Х	X		
Spot urine (creatinine/albumi n ratio) or urine dipstick for protein 	x		X	X	X	X	X	X	X	X	X	X	X	X		
LTFU data															X	X
Obtain archived Diagnostic samples		x														-

- 1. Screening: May start 60 days post-CAR-T, but must be completed within 30 days prior to enrollment. Consent may occur at any time prior to screening period and does not count within the 30-day time window requirement. Subjects will be enrolled in the trial within 30 days of screening procedures (consent not included) and start treatment within the 90–120 days window after anti-BCMA CAR-T.
- 2. Screening ocular examination to be performed by an ophthalmologist (or an optometrist, if an ophthalmologist is not available) within 30 days prior to enrollment. See Sections 5.2.4 and 5.3 for lists of ophthalmic exam procedures. On treatment, ocular exams are to be performed prior to each dosing of belantamab mafodotin until the 70-day safety visit. In case of persistent or newly developed ocular symptoms or vision changes, participants will have further ophthalmologic exams, at least every three months until resolution (to grade 1 or baseline) or more frequently as clinically indicated by the eye care specialist or up to one year (whichever comes first). Ocular exam may be performed up to five days prior to second dose onwards for belantamab mafodotin.
- 3. Continuously, adverse event (AE) assessments: AEs should be documented and recorded at each visit using the National Cancer Institute Common Terminology Criteria for Adverse Events (NCI CTCAE) version 5.0. SAEs and AEs will be collected and reported after first treatment dose, through 70 days post last dose of belantamab mafodotin..
- 4. Concomitant treatments: All concomitant treatments, blood products, as well as nondrug interventions received by subjects will be recorded on the eCRF from screening through end of study.
- 5. Hematology includes complete blood count (CBC) with differential.

Short Title: MCW EMBRACE TRIAL

- 6. Chemistry: alanine aminotransferase (ALT), albumin, alkaline phosphatase, aspartate aminotransferase (AST), bicarbonate, total bilirubin, blood urea nitrogen (BUN), chloride, serum calcium, creatinine, glucose, lactate dehydrogenase, magnesium, sodium, phosphorus or phosphate, and potassium.
- 7. For subjects with serologic evidence of resolved HBV infection (i.e., positive anti-HBs or positive anti-HBc) at screening, HBV DNA testing by PCR must be performed locally Q12W during treatment, at the end-of-treatment visit, and Q12W for up to six months after the last dose of study treatment. HBV DNA is not necessary for patients positive for anti-HBs, but negative for anti-HBc and with a history of hepatitis B vaccination.
- 8. Perform only in women of childbearing potential (WOCBP). Two serum pregnancy tests should be performed prior to treatment: at screening prior to enrollment and within 72 hours prior to C1D1. Other pregnancy tests may be either serum or urine. For questionable cases, follicle-stimulating hormone (FSH) and estradiol (as needed in women of non-childbearing potential only) should be performed at local lab. Final pregnancy test (serum or urine) must be performed in WOCBP at least 70 days after the last dose of belantamab mafodotin, preferably at a visit, or via a urine pregnancy test kit mailed to the participant's home with results reported by telephone. Follow-up pregnancy assessment by telephone (for WOCBP only) should be performed four months after the last dose of belantamab mafodotin.
- 9. Subjects will be enrolled in the trial within 30 days of screening procedures (consent not included) and start treatment within the 90–120 days window after anti-BCMA CAR-T. Each cycle is eight weeks +/- three days. If treatment cycle cannot be resumed within 16 weeks of the previous cycle (from day 1), the patient may permanently discontinue belantamab mafodotin treatment on the trial.
- 10. 70-day post-last dose safety visit due to half-life of belantamab mafodotin side effect profile: within 70 days +/- three days of last dose. Treatment may continue until discontinuation due to AEs, completion of 12 cycles, progression of myeloma, or beginning of a subsequent anti-myeloma therapy.
- 11. UPEP with urine immunofixation: Necessary only when M-spike in urine is main parameter for response assessment (based on screening assessment), and will be completed on day 1 of cycles two, four, six, eight, 10, 12, and at end of study. After day 0, if urine M-protein is 200 mg/24 hour, 24-hour urine collections can be stopped, except to determine/confirm M-protein is <100 mg/24 hours for VGPR or undetectable for CR.
- 12. Imaging of bones for lytic lesions by method aligned with institutional guidance (skeletal survey, CT, or MRI).
- 13. For patients with extramedullary disease, imaging is only required by either CT, MRI, or PET/CT per local guidance. Needs to be performed by the same method throughout the study as was done at baseline. Selected target lesion needs to be measured and followed over time. Plasmacytoma measurements should be taken from the CT portion of the PET/CT, or MRI scans, or dedicated CT scans. Skin lesions, if present, should be measured with a ruler. Measurement of tumor size will be determined by the sum of the products of the maximal perpendicular diameters of measured lesions (SPD).

- 14. Whole-body PET-CT must performed at screening. Whole-body PET-CT should be repeated if positive for disease at the time of screening, and repeated at the next BM timepoints (e.g., Cycle 3 Day 1, and Cycle 7 Day 1 if not negative at the Cycle 3 Day 1 timepoint). Whole-body PET-CT will be performed during/after treatment to confirm MRD-negativity if MRD-positive at screening/prestudy (if FDG-avid extramedullary lesions are seen at screening).
- 15. This assessment will include morphology, flow cytometry, FISH for myeloma-associated abnormalities and sample to be sent to Adaptive Biotechnologies for identification of myeloma-specific sequences. Fluorescence *in situ* hybridization (FISH) testing to be performed locally at least for t(4;14), t(14;16), amp(1q), del(1p) and del(17p13). If participant is known to have tested positive for t(4;14) or t(14;16) on previous tests regardless of timeframe, FISH for these translocations does not need to be repeated. FISH results from samples taken within 90 days prior to first dose are acceptable. Samples are also to be obtained/sent for correlative studies (refer to Appendix 5).
- 16. NGS for MRD assessment (clonoSEQ®) will be performed on bone marrow aspirate sample. Bone marrow aspiration with MRD assay (first pull, in subjects found to be MRD-informative based on clone identification sample) and flow cytometry/cytotoxicity assays will be performed within seven days before cycle 3 day 1, and cycle 7 day 1 and within seven days before or after cycle 12 day 56. Samples are also to be obtained/sent for correlative studies (refer to Appendix 5).
- 17. Patient-reported outcomes (refer to Appendix) PRO assessments should be completed before any other study procedures are performed (except for blood draws).:
  - a. EORTC-QLQ-MY20 and EORTC QLQ-C30
    - i. Collect at cycle 1 day 1 (prior to treatment), cycle 3 day 1, cycle 7 day 1, cycle 9 day 1, and 70-day safety visit.
  - b. OCULAR SURFACE DISEASE INDEX (OSDI)
    - i. Collect at cycle 1 day 1 (prior to treatment), every cycle day 1, and 70-day safety visit.
- 18. For patients who discontinue treatment prior to progression, continue standard-of-care follow-up every three months until progression or start of another treatment (whichever comes first), then continue to long-term follow-up.
- 19. Long-term survival data collected/reported approximately every six months (+/- 30 days).
- 20. Urine dipstick for protein may be used to assess for presence of urine protein. Albumin/creatinine ratio needs to be done in any participant with urine dipstick result of ≥1+ at screening, or with positive protein if urine dipstick protein quantification is not available.

Short Title: MCW EMBRACE TRIAL 15 Version No.: 3
Version Date: 12/29/2022

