#### 3.3 Estimated Time for Completion of Study Enrollment

The study will reach primary enrollment completion in approximately 24 months from the time the study opens to accrual.

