#### 3.4 Estimated Time for Study Completion

The study will reach study completion in approximately nine years (four years for completion of treatment for all patients, and five years of long-term survival follow-up) from the time the study opens to accrual.

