#### 4.10 End of Study Definition

A participant is considered to have completed the study if he or she completed all phases of the study, including the last visit or the last scheduled procedure shown in the calendar of events or has been discontinued.

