#### **5 TREATMENT PLAN**

#### 5.1 Treatment

Subjects will receive belantamab mafodotin as maintenance therapy. Belantamab mafodotin will be administered IV over approximately 30 minutes at the recommended dose of 1.9 mg/kg IV day 1 of every 56-day cycle (+/- 3 days).

Maintenance therapy with belantamab mafodotin will continue until progressive disease (PD), death, unacceptable toxicity, withdrawal of consent or end of study, whichever occurs first. Dose interruptions or reductions may be required to address potential drug-associated toxicities.

The dose to be administered will be based on actual body weight calculated at baseline (cycle 1 day 1). However, if the change in body weight is greater than 10%, the dose will be recalculated based on the actual body weight at the time of dosing. The dose may be reduced to address toxicity as described in Section 5.2.

Arm	Belantamab mafodotin (Day 1 of every 56-day cycle)	
A	1.9 mg/kg IV over at least 30 minutes	

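### Section 5.1 and the protocol summary set no cycle limit on maintenance treatment, while study calendar footnote 10 stops it at 12 cycles

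*Combined protocol and SAP*

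**What the plan says.** Three places bear directly on when treatment stops.

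- Section 5.1 (Treatment): maintenance "will continue until progressive disease (PD), death, unacceptable toxicity, withdrawal of consent or end of study", whichever comes first. No number of cycles is given.
- Protocol summary, Study Intervention Description: the same sentence, "Maintenance therapy with belantamab mafodotin will continue until progressive disease (PD), death, unacceptable toxicity, withdrawal of consent or end of study".
- Study calendar (Table 1), footnote 10: "Treatment may continue until discontinuation due to AEs, completion of 12 cycles, progression of myeloma, or beginning of a subsequent anti-myeloma therapy".

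The hypothesis in Section 2 describes maintenance lasting until progression, and the list of stopping reasons in Section 4.7 contains no cycle count.

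Other parts of the plan look like a 12-cycle regimen. The dosing row of the calendar ends at C12D1. Footnote 16 places the last marrow "within seven days before or after cycle 12 day 56". The summary allows about "2 years for completion of treatment for all patients" after about three years of enrollment. Section 3.4 allows "four years for completion of treatment for all patients", counted from opening, and Section 3.3 states "The study will reach primary enrollment completion in approximately 24 months".

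Section 8.3 gives two timelines. Its first paragraph has 29 months of enrollment, then 11 months to the last subject's last dose and assessment, about 40 months in total. Its second paragraph allows five years from opening for all patients to complete treatment.

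**The concern.** Section 5.1 is the dosing instruction. For a patient who finishes cycle 12 without progression and tolerates the drug, it says to keep dosing, while footnote 10 says to stop. Two sites could treat the same patient differently and each be following the protocol.

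A patient dosed beyond cycle 12 would have no calendar visit to attend. Table 3a needs laboratory values at dosing: its platelet rule applies on dosing days, its afebrile neutropenia rule applies on day 1 of any cycle, and it also has creatinine and urine-protein rules. None of these tests is scheduled after C12D1 for a patient still on treatment. The three-monthly pre-progression column is for patients who have already stopped (footnote 18).

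The rule also fixes the date of last dose, which starts the 70-day adverse-event window and the contraception periods. It determines the drug exposure behind the longer-term descriptive results: PFS, duration of response, overall survival and toxicity.

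**Working it through.** **1. Does the end-of-study clause supply the cap?** Section 4.10 ties a participant's completion to all phases, "including the last visit or the last scheduled procedure shown in the calendar of events", or to discontinuation. The last calendar column is long-term follow-up. Sections 3.1 and 5.8 continue six-monthly survival follow-up until the end of the study. On these texts the end of the study comes years after cycle 12.

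**2. Does the conflict reach the primary endpoint?** First dose is at day 90 to 120 after CAR-T and cycles last 56 days.
- Start at day 90: doses on days 90, 146, 202, 258 and 314; the sixth falls on day 370.
- Start at day 120: doses on days 120, 176, 232, 288 and 344; the sixth falls on day 400.

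Five scheduled doses fall by day 365 under either rule, so the 12-month comparison with 54% is untouched.

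**3. How many patients could reach dose 13?** Dose 13 would be due 12 × 56 = 672 days after first dose, which is 672 / 30.44 = 22.1 months (day 90 + 672 = 762 to day 120 + 672 = 792 after CAR-T). The plan's conditional PFS covers the 9 months from month 3 to month 12: 54% under the null, 74% under the alternative (Section 8.2), with exponential PFS assumed. Extending that constant hazard:
- Null: 0.54^(22.08/9) = 0.221; × 45 = 9.9 patients.
- Alternative: 0.74^(22.08/9) = 0.478; × 45 = 21.5 patients.

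Sensitivity, with an assumed decreasing hazard (Weibull shape 0.7, same 9-month values), where (22.08/9)^0.7 = 1.874:
- Null: 0.54^1.874 = 0.315; × 45 = about 14 patients.
- Alternative: 0.74^1.874 = 0.569; × 45 = about 26 patients.

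Neither calculation removes anyone for toxicity, withdrawal or delay.

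**4. Section 8.3's own figures.** Enrollment is 12 subjects in year 1, then 33 at two a month: 12 + 33/2 = 28.5, or about 29 months, as stated. The sum 29 + 11 = 40 also reproduces. The 11 months does not: 11 × 30.44 / 56 = 6.0 cycles, half the regimen. The second paragraph leaves 60 − 29 = 31 months after enrollment, against 11 in the first.

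**5. Timeline under the cap, at nominal 56-day spacing.**
- Last dose (C12D1): 11 × 56 = 616 days = 20.2 months after first dose.
- 70-day safety visit: 616 + 70 = 686 days = 22.5 months after first dose.

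| Accrual duration | Source | Last 70-day visit, months from opening |
|---|---|---|
| 24 months | Section 3.3 | 24 + 22.5 = 46.5 |
| 29 months | Section 8.3 | 29 + 22.5 = 51.5 |
| about 36 months | Summary | 36 + 22.5 = 58.5 |

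Enrollment can occur from day 60 and first dose as late as day 120, so a lag of 0 to 60 days (0 to 2.0 months) comes on top. The first row is close to Section 3.4's four years and the third to five years. Only the 40 months is out of line with 12 cycles.

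**The case against.** The best defense is that the cap is already readable. Footnote 10 states it, there is no C13 column, and the calendar uses end of study loosely for an earlier point. Footnote 4 records concomitant treatments until then although that row stops at the 70-day visit, footnote 11 schedules urine electrophoresis at that point although the row has no long-term follow-up entry, and the abbreviation list defines EOS as a visit. So Section 5.1 could be taken to mean the end of the 12-cycle schedule. This shows that the term is ambiguous, and it makes 12 cycles the likelier intent. It does not settle the matter, because Sections 3.1, 4.10 and 5.8 all place the end of the study after survival follow-up.

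A reader might also infer that patients beyond cycle 12 would be dosed without safety oversight. The documents do not support that. Eye examinations are required before every dose (footnote 2, Section 5.2.4), so the main known hazard stays covered. Disease evaluation continues at least every 56 days (Section 3.1). Table 3a presupposes dosing-day counts at any cycle. What is missing is the scheduled hematology, chemistry and urine protein.

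On Section 8.3, one might read the 11 months as time to the primary analysis. That fails: the sentence names the last dose, and a subject enrolled at day 60 to 120 reaches day 365 in 245 to 305 days (8 to 10 months). It is fair, however, that this is an administrative forecast that changes no dose, analysis or decision.

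**Conclusion.** The treatment section and the calendar give incompatible stopping rules, and following Section 5.1 as written changes what progression-free patients receive after cycle 12. It is worth correcting because the repair is small and the text governs dosing. The primary 12-month test, the sample size of 45 and the power do not depend on it; the affected outcomes are secondary and descriptive.

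The figure of roughly 10 to 21 of 45 patients is illustrative. It might be read as a ceiling because nobody is removed for toxicity, withdrawal or delay, but it rests on a constant hazard carried from 9 to 22 months. The assumed decreasing hazard gives about 14 to 26, and Section 8.2.3 itself considered non-exponential survival.

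The Section 8.3 figures are a secondary error: 11 months holds about six cycles, and 40 months conflicts with the five years that follow. The replacement figures of 22.5 and about 52 months are minimums, not forecasts. They assume no dose delay, whereas footnote 9 contemplates gaps of up to 16 weeks between cycles.

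**What to change.** If 12 cycles is intended, add *or completion of 12 cycles* to the treatment sentence in Section 5.1 and to its copy in the protocol summary, and align the wording of Sections 2 and 4.7. If open-ended treatment is intended, delete the cap from footnote 10 and add a repeating post-C12 dosing visit to the calendar with the hematology, chemistry and urine protein that Table 3a needs.

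Under the cap, also correct Section 8.3. State at least about 22.5 months from the last subject's first dose to the 70-day visit, and at least about 52 months in total with 29 months of enrollment, both before dose delays. Use one accrual duration throughout, since 24, 29 and about 36 months now appear, and reconcile the years to treatment completion with it.

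The cost is one phrase in two places, two consistency edits and a few timeline figures, or one calendar column if treatment is open-ended. The sample size, power and primary analysis do not change.
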